4.4.3 Presentation of results

Analyses will be done for ADA against efgartigimod and antibodies against rHuPH20.

Frequency tabulations (number and percentages) will be provided with ADA or rHuPH20 Ab negative/positive/unevaluable samples per analysis visit. These tables will be presented by ADA or rHuPH20 Ab participant category.

Frequency tabulations (number and percentages) will be provided by treatment on:

- Participants per ADA or rHuPH20 Ab participant classification
- Prevalence and incidence of ADA or rHuPH20 Ab
- ADA or rHuPH20 Ab unevaluable participants
- ADA or rHuPH20 Ab baseline positive/negative samples

[figure not shown]
For details on the definitions, see the above section 4.4.2.1. and 4.4.2.2.

The above frequency tabulations will be repeated for NAb assay using the definitions as defined in section 4.4.2.3. and 4.4.2.4.

In addition, a frequency tabulation (number and percentages) will be provided for:

- NAb against efgartigimod positive participants within the ADA participant classification (Treatment-unaffected ADA, Treatment-induced ADA, Treatment-boosted ADA, ADA Negative, ADA Unevaluable)
- NAb against rHuPH20 Ab positive participants within the rHuPH20 Ab participant classification
- rHuPH20 Ab positive participants within efgartigimod ADA participant classification

Correlation tables by ADA and NAb participant classification against efgartigimed and by rHuPH20 Ab will be provided for the following parameters:

[figure not shown]

- Mean (SD) drug concentration over time
- Mean (SE) percent change from baseline in total IgG
- Overall Treatment-Emergent Adverse Events by MedDRA System Organ Class and Preferred Term by Overall Anti-Drug Antibodies Participant Classification (All Participants)
- Overall Serious Treatment-Emergent Adverse Events by MedDRA System Organ Class and Preferred Term by Overall Anti-Drug Antibodies Participant Classification (All Participants)
- Overall Injection related reactions (IRR) by Overall Anti-Drug Antibodies Participant Classification (All Participants)
- Overall Injection site reactions (ISR) by Overall Anti-Drug Antibodies Participant Classification (All Participants)
- Proportion of participants being in CRoff at week 36*
- * Difference in proportion responders (primary endpoint) between each of the 4 categories versus ADA Negative, NAb baseline neg post-baseline neg and rHuPH20 Ab Negative, including 95% exact confidence interval will be calculated.

Correlation tables by NAb against efgartigimod participant classification only need to be provided as soon as there are $N \ge 5$ participants in the sum of baseline negative – postbaseline positive and baseline positive – postbaseline positive NAb positive categories in (one of) the treatment arms. Correlation tables of mean drug concentration over time, correlation with efficacy, and mean percent change from baseline in total IgG can be restricted to the efgartigimod-administered participants only. The other correlation tables must be provided for efgartigimod- and placeboadministered participants.

ADA titer values against efgartigimod and rHuPH20 Ab titer values will be summarized by means of descriptive statistics by ADA participant classification or rHuPH20 Ab participant classification, respectively.

All available data on ADA and NAb against efgartigimod, rHuPH20 Ab and rHuPH20 NAb will be listed, showing also the sample status and participant classification.

5. SAFETY ANALYSES

5.1 ADVERSE EVENTS

5.1.1 Available data

Adverse events (AEs) are coded into system organ classes and preferred terms using the latest version of the MedDRA available at the database lock. For each AE, start and stop date/times are collected as well as severity according to the National Cancer Institute (NCI) common terminology criteria for adverse events (CTCAE) toxicity grading list (version 5.0), a seriousness flag, treatment relatedness, relatedness to procedures, action taken towards the IMP, outcome, and AE of special interest (AESI) category (infection).

5.1.2 Derivation rules

Treatment-emergent adverse events (TEAE) are defined as AEs starting within 60 days of an administration of IMP. Post-TEAEs are AEs starting after first administration of IMP that are not TEAEs.

Based on their start date/time, AEs will be allocated to the phase during which they started. Each AE will therefore be reported in only one phase. In case the AE start date/time is incomplete or missing and the AE could consequently be allocated to more than one phase, a worst-case allocation will be done as detailed below:

 Treatment phase vs. non-treatment phase: the AE will be allocated to the treatment phase unless the available parts of the AE start or stop date/time provide evidence for allocating to the non-treatment phase.

A death case is defined as an AE with outcome 'fatal'.

An AE for which the IMP was discontinued is defined as an AE with action taken 'drug withdrawn'.

AEs with missing treatment, prednisone or procedure relatedness will be considered as treatment-related, prednisone-related, or procedure-related respectively.

[figure not shown]
AEs with missing seriousness will be considered as serious AEs.

Adverse events of special interest will be defined using MedDRA system organ class 'Infections and infestations'.

Injection-related reactions (IRRs) will be defined as all AEs with MedDRA preferred terms that are listed in either:

- Hypersensitivity standardized MedDRA query (SMQ) (broad selection)
- Anaphylactic reaction (SMQ) (broad selection)
- Extravasation events (injections, infusions and implants) (SMQ) (broad selection), excluding implants

AND occurring within 48 hours of an administration, or within 2 days in case no AE start time is available. In case of (partially) missing AE start date, the AE will be considered as an IRR, unless the available parts of the AE start date provide evidence it did not occur within 48 hours of an injection.

Injection site reactions (ISR) will be defined as all AEs with a MedDRA high level term of "Injection site reaction", regardless of the time of AE onset relative to an administration.

AE onset and duration will be calculated as follows when start and stop dates are fully known:

- AE onset day (vs. first administration) =
 - AE start date ≥ date of first administration: AE start date date of first IMP administration + 1 day
 - AE start date < date of first administration: AE start date date of first IMP administration
- AE duration (days) =
 - AE end date AE start date + 1 day
 - Study completion date or Study discontinuation date AE start date + 1 day (when the AE start date is fully known but the AE is not resolved at the end of the study)

In this case the duration will be presented as ">x days".

Event rates per 100 participant years of follow-up (PYFU) will be calculated as 100*number of events/PYFU, with:

- PYFU overall (in years) will be calculated as [the sum over all participants of the study duration calculated as (last phase end date – first IMP date + 1 day)]/365.25.
- PYFU for TEAEs (in years) will be calculated as above for PYFU overall with study duration cut off at 60 days after last IMP (i.e., last IMP date + 60 included) since AEs starting more than 60 days after last administration of IMP are not considered as TEAE.
- PYFU for post-TEAEs (in years) will be calculated as [the sum over all participants of all period durations during which an AE is considered to be post-treatment-emergent]/365.25.

Time to onset of first treatment-emergent adverse event (in days) will be calculated as date of the first treatment-emergent AE – date of first IMP administration + 1.

Participants without any TEAE will be censored at the date of the last IMP administration + 60 days or end date of the last analysis phase, whichever comes first. This info will be provided in the ADaM dataset (ADTTE); no tabulation is foreseen.

Similar time-to-event calculations will be done for:

- Time to onset of first serious TEAE
- Time to onset of fatal TEAE

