7.1. IMP Discontinuation

7.1.1. Permanent Discontinuation

Permanent discontinuation of IMP occurs when the participant stops receiving IMP before the end of the study, and does not resume receiving IMP. The participant also must not have withdrawn informed consent.

The investigator will document the primary reason for early discontinuation of IMP.

Participants who permanently discontinue IMP will be encouraged to remain in the study and attend mandatory on-site visits as specified in the SoA (Table 1). If the participant cannot attend these visits for any reason, the study site will perform an early study discontinuation (ESD) visit and safety follow-up visits as specified in the SoA (Table 1).

Unless consent from the study has been withdrawn, the participant will attend an early treatment discontinuation (ETD) visit. Study sites will attempt to perform the ETD visit within 7 days after the participant's final IMP administration. After the ETD, the participant will continue participation in the study through the rest of the 36-week treatment period and may receive rescue therapy (defined in Section 6.8.3). At week 36, the participant will complete the EoTP visit assessments (Table 1). If the participant meets rollover eligibility requirements (described in the ARGX-113-2010 protocol) at the end of the EoTP visit, they will be invited to immediately enroll in the OLE study ARGX-113-2010. If the participant does not meet rollover eligibility requirements or chooses not to enroll in the OLE study, they will participate in the 7-week treatment-free follow-up period. Refer to the SoA (Table 1) for data to be collected at the time of discontinuation of IMP and follow-up and for any other evaluations that need to be completed.

The following circumstances will result in the permanent discontinuation of IMP:

- Participant becomes pregnant or intends to become pregnant (refer to Section 8.4.6).
- Investigator decides that discontinuing IMP is in the participant's best interest (the sponsor will be informed).
- Participant develops an SAE or AE that contraindicates further administration of IMP in the investigator's opinion.
- Unblinding occurred.
- Participant exhibits any of the conditions outlined in Section 6.8.3. In these cases, participant may start rescue therapy.
- Any of the liver chemistry criteria resulting in temporary IMP discontinuation outlined in Section 7.1.2 is met, and the event is considered by the investigator to be related to the IMP.

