8.4.4. Reporting of AEs and SAEs

All AEs that occur during the study, from signing of the ICF until the EoTP or the last follow-up visit, are to be recorded on the appropriate AE pages (either "serious" or "nonserious") of the eCRF. The investigator should complete all the details requested, including date of onset, time of onset, stop date (when applicable), stop time (when applicable), severity, action taken, outcome, and relationship to IMP, to corticosteroid (non-IMP) use, and to study procedures. Each event should be recorded separately on the eCRF.

Any SAE, including death due to any cause, which occurs during this study after the signing of the ICF, whether or not related to the IMP, must be reported immediately (within 24 hours of the study site's knowledge of the event). Further information on follow-up procedures is provided in Section 8.4.3 and Section 10.3.

The report will contain as much available information concerning the SAE as possible, to enable the sponsor (or an authorized representative) to file a report, which satisfies regulatory reporting requirements. These timelines apply to initial reports of SAEs and to all follow-up reports.

Criteria for documenting the relationship to IMP and severity, outcome, and action taken will be the same as those previously described.

All SAEs that are spontaneously reported within 30 days after the last study visit are to be collected and reported in the safety database, and all efforts should be made to follow-up until resolution.

Additional follow-up information should be completed and entered on a paper SAE report form and sent by fax/email to the sponsor's designee.

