5.1.3 Presentation of results

Unless mentioned otherwise, tables will present TEAEs only.

The TEAE tables will be presented for the treatment and follow-up phase combined.

SGS	Statistical Analysis Plan	
ARGX-113-2009	Final and Interim Analysis	Final 4.0 of 04NOV2024

An overview table will show the number and percentage of participants with at least one event and the number of events and number of events per 100 participant years of follow-up for the following:

- TEAEs
- Treatment-related TEAEs
- Serious TEAEs
- Serious treatment-related TEAEs
- Serious prednisone-related TEAEs
- Grade ≥ 3 TEAEs
- Treatment-related Grade ≥ 3 TEAEs
- TEAEs related to prednisone (or equivalent OCS)
- TEAEs related to study procedures
- TEAEs for which the IMP was discontinued
- TEAEs for which the IMP was interrupted
- TEAEs of special interest
- Treatment-related TEAEs of special interest
- TE IRRs
- Serious TE IRRs
- TE ISR events
- Fatal TEAEs

This overview table will be repeated for:

- Post-TEAEs (AEs starting after first IMP administration but not considered treatment-emergent)
- All AEs during the treatment + follow-up phase (overall AEs)

A similar overview table will be created specifically for treatment-emergent ISR events and will show the number and percentage of participants with at least one event, the number of events and number of events per 100 participant years of follow-up for the following:

- Treatment-emergent ISRs (TEISRs)
- Treatment-related TEISRs
- Serious TEISRs
- Serious treatment related TEISRs
- Serious prednisone related TEISRs
- Grade ≥ 3 TEISRs
- Treatment-related Grade ≥ 3 TEISRs
- TEISRs related to prednisone (or equivalent OCS)
- TEISRs related to study procedures
- · TEISRs for which the IMP was discontinued

SGS	Statistical Analysis Plan	
ARGX-113-2009	Final and Interim Analysis	Final 4.0 of 04NOV2024

TEISRs for which the IMP was interrupted

[figure not shown]
A summary table of TEAEs by MedDRA system organ class and preferred term will show the number and percentage of participants with at least one event, the number of events and number of events per 100 participant years of follow-up.

This summary table will be repeated for:

- Post-TEAEs (AEs starting after first IMP administration but not considered treatment-emergent)
- All AEs during the treatment + follow-up phase (overall AEs)

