Separate tables by MedDRA system organ class and preferred term will be prepared for the following, showing the number and percentage of participants with at least one event, the number of events and number of events per 100 participant years of follow-up:

- Treatment-related TEAEs
- Serious TEAEs
- Serious treatment-related TEAEs
- Serious prednisone-related TEAEs
- Grade ≥ 3 TEAEs
- Treatment-related Grade ≥ 3 TEAEs
- TEAEs related to prednisone
- TEAEs related to study procedures
- TEAEs for which the IMP was discontinued
- TEAEs of special interest
- Treatment-related TEAEs of special interest

- TE IRRs
- Serious TE IRRs
- TE ISR events
- Fatal TEAEs
- Common TEAEs (preferred terms occurring in at least 10% [5% for the
 analyses using pooled Part A and Part B data] of participants in either
 treatment group; the cut-off is applied after rounding to the nearest
 integer. System organ class will be presented if any preferred term
 within is selected.)

All AEs, including pre-treatment events will be listed. Furthermore, separate listings will be created for SAEs, fatal AEs, TEAEs leading to discontinuation of IMP and AESIs. A coding listing will indicate how individual terms have been coded to MedDRA system organ classes and preferred terms.

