14.3.1.3	Treatment-Related Treatment-Emergent Adverse Events by MedDRA System Organ Class and Preferred Term	SAF	
14.3.1.4	Serious Treatment-Emergent Adverse Events by MedDRA System Organ Class and Preferred Term	SAF	L
14.3.1.5	Serious Treatment-Related Treatment-Emergent Adverse Events by MedDRA System Organ Class and Preferred Term	SAF	

SGS	Statistical Analysis Plan	
ARGX-113-2009	Final and Interim Analysis	Final 4.0 of 04NOV2024

14.3.1.6	Serious Prednisone-Related Treatment-Emergent Adverse Events by MedDRA System Organ Class and Preferred Term	SAF	
14.3.1.7	Grade 3 or More Treatment-Emergent Adverse Events by MedDRA System Organ Class and Preferred Term	SAF	TL
14.3.1.8	Treatment-Related Grade 3 or More Treatment- Emergent Adverse Events by MedDRA System Organ Class and Preferred Term	SAF	
14.3.1.9	Prednisone-Related Treatment-Emergent Adverse Events by MedDRA System Organ Class and Preferred Term	SAF	TL
14.3.1.10	Procedure-Related Treatment-Emergent Adverse Events by MedDRA System Organ Class and Preferred Term	SAF	
14.3.1.11	Treatment-Emergent Adverse Events Leading to Discontinuation of IMP by MedDRA System Organ Class and Preferred Term	SAF	TL
14.3.1.12	Treatment-Emergent Adverse Events of Special Interest by MedDRA System Organ Class and Preferred Term	SAF	TL
14.3.1.13	Treatment-Related Treatment-Emergent Adverse Events of Special Interest by MedDRA System Organ Class and Preferred Term	SAF	TL
14.3.1.14	Treatment-Emergent Injection-Related Reactions by MedDRA System Organ Class and Preferred Term	SAF	TL
14.3.1.15	Serious Treatment-Emergent Injection-Related Reactions by MedDRA System Organ Class and Preferred Term	SAF	TL
14.3.1.16.1	Treatment-Emergent Injection Site Reactions - Overview	SAF	TL
14.3.1.16.2	Treatment-Emergent Injection Site Reactions by MedDRA System Organ Class and Preferred Term	SAF	TL
14.3.1.17	Fatal Treatment-Emergent Adverse Events by MedDRA System Organ Class and Preferred Term	SAF	TL
14.3.1.18	Common Treatment-Emergent Adverse Events by MedDRA System Organ Class and Preferred Term	SAF	TL
LABORATORY D	ATA		
14.3.2.1	Descriptive Statistics of Laboratory Test Actual Values and Changes from Baseline	SAF	
14.3.2.2	Descriptive Statistics of Albumin and Low-Density Lipoprotein-Cholesterol (LDL-C) Actual Values,	SAF	

[figure not shown]

1			_
	Changes from Baseline and Percent Changes from Baseline		
14.3.2.3	Cross-Tabulation of Laboratory Abnormalities Versus Baseline Over Time	SAF	

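### The two by-term tables of prednisone-related adverse events stop 60 days after the last IMP dose and, unlike the overview and the all-cause by-term summary, are not repeated for later events

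*SAP*

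**What the plan says.** SAP 5.1.2 defines the window by IMP dosing: "Treatment-emergent adverse events (TEAE) are defined as AEs starting within 60 days of an administration of IMP". Anything later is a separate category: "Post-TEAEs are AEs starting after first administration of IMP that are not TEAEs". Person-time for TEAE rates is cut at the same point ("last IMP date + 60 included"). The same section also defines person-time for post-TEAEs and overall.

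SAP 5.1.3 sets the default for the tables: "Unless mentioned otherwise, tables will present TEAEs only". It then makes two exceptions. The overview table, which has rows for prednisone-related and serious prednisone-related events, is repeated for post-TEAEs and for all events in the treatment and follow-up phases. So is the all-cause summary by system organ class and preferred term. The list of separate by-term tables that follows, which includes "TEAEs related to prednisone" and the serious subset, has no such repeat. SAP 8.1 agrees: 14.3.1.9 is titled "Prednisone-Related Treatment-Emergent Adverse Events by MedDRA System Organ Class and Preferred Term" and marked for topline, and 14.3.1.6 is the serious counterpart, not marked for topline.

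On the data side, Protocol 8.4.4 has the investigator record, for each event up to the EoTP or last follow-up visit, the "relationship to IMP, to corticosteroid (non-IMP) use, and to study procedures". Under Protocol 6.8.1.3 and 6.8.3, treatment failure leads to permanent IMP discontinuation, and rescue therapy may include oral corticosteroids. Protocol 7.1.1 encourages these participants to remain, and after the early treatment discontinuation visit "the participant will continue participation in the study through the rest of the 36-week treatment period and may receive rescue therapy".

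**The concern.** A window of last IMP dose plus 60 days suits a question about efgartigimod. The two prednisone-related tables ask about a different drug, whose exposure can continue after IMP stops. The participants for whom the two exposures separate most are the treatment failures. By the definition in Protocol 4.1.3 they have already had an escalated steroid dose, they stop IMP early, and they may then receive more oral corticosteroid.

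Assessing glucocorticoid-associated morbidity is a stated objective in both parts. The other planned steroid summaries do not cover this period either. The composite Glucocorticoid Toxicity Index scores use only assessments up to the start of rescue therapy (SAP 4.1.4, item 17), and the normalized cumulative OCS dose is confined to the on-IMP period (SAP 4.1.3.1, item 1). The adverse event tables are therefore the main planned summary that could describe steroid harm after rescue starts. If early failures are unequal between arms, the by-term prednisone-related percentages lose more events from the arm with more failures.

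**Working it through.** The plan states no figure for this, so the check is day arithmetic.

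**Inputs**
- Study day = 7 × week + 1. Week 36 is day 253 (both schedules of activities) and week 43 is day 302.
- Last planned IMP dose: week 35, day 246 (Protocol Table 1, IMP footnote).
- TEAE window closes on the last IMP day + 60 (SAP 5.1.2).
- Timing of treatment failure (Protocol 6.8.1.3): 1 to 3 weeks at the starting dosage, then up to 3 weeks escalated, with 1 optional further week. The range runs from 1 + 3 = week 4 to 3 + 3 + 1 = week 7.
- Assumption: the last IMP dose for such a participant falls at weeks 3 to 7. Week 3 allows for failure being declared at week 4 before that week's dose.

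**Formula**

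Uncovered days = max(0, end of follow-up − (last IMP day + 60)), as a share of the end-of-follow-up day.

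| Last IMP | Day | Window closes | Uncovered to week 36 (day 253) | Uncovered to week 43 (day 302) |
|---|---|---|---|---|
| Week 3 | 22 | 82 | 171/253 = 68% | 220/302 = 73% |
| Week 4 | 29 | 89 | 164/253 = 65% | 213/302 = 71% |
| Week 6 | 43 | 103 | 150/253 = 59% | 199/302 = 66% |
| Week 7 | 50 | 110 | 143/253 = 57% | 192/302 = 64% |
| Week 20 | 141 | 201 | 52/253 = 21% | 101/302 = 33% |
| Week 35 | 246 | 306 | 0 | 0 |

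The week 43 column applies only to participants who do not roll over to the extension study and complete follow-up.

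**Break-even.** More than half of follow-up is uncovered when the last IMP day is before 253/2 − 60 = 66.5 (about week 9) for follow-up to week 36, or before 302/2 − 60 = 91 (about week 13) for follow-up to week 43.

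**Where a late prednisone-related event is shown**

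| Display | Event more than 60 days after last IMP |
|---|---|
| Overview, prednisone-related rows | Yes, in the post-TEAE and overall repeats |
| All-cause by-term summary (14.3.1.2) | Yes, but not split by prednisone relationship |
| Listing of all adverse events | Yes |
| 14.3.1.6 and 14.3.1.9 | No |

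**Effect on the statistics in the two tables.** Percentages divide by all participants in the analysis set (SAP 2.4.1), so a participant whose window closes at day 82 to 110 still counts in full in the denominator while later events are not counted. Rates per 100 participant-years use person-time cut at the same point as the events, so they are not lowered mechanically. They describe the period inside the window and are silent on the rest.

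**The case against.** The strongest case against is that little is hidden. Late prednisone-related events are counted in the repeated overview, shown by term in the all-cause repeats and listed individually. A reader might infer from the titles of the two tables that late steroid harm leaves the by-term reporting altogether; SAP 5.1.3 and the entry for 14.3.1.2 in SAP 8.1 show that it does not. A reader might also infer that the event rates are biased downward. The matched person-time in SAP 5.1.2 rules that out unless the event rate is higher after the window closes, and nothing in the documents says that it is.

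Other parts of the objection also stand. The escalated steroid course comes before failure is declared, so it and about 60 further days are inside the window. A steroid toxicity event during IMP treatment that itself triggers discontinuation is a TEAE. The glucocorticoid objective has its own endpoints, and these two tables are descriptive. Different totals in a treatment-emergent table and an overall overview are expected from their titles and are not an inconsistency. No failure rate is given, so the effect on a whole table cannot be calculated, and an excess of failures on placebo is a supposition.

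The objection does not dispose of the gap. The SAP already judged that the overview and the all-cause summary need post-TEAE and overall versions. The two tables devoted to a drug that can continue after IMP stops have at least as good a claim. As planned, the overall overview would give a count of prednisone-related events with no matching by-term table to say what they were.

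**Conclusion.** The point holds in a limited form. Tables 14.3.1.6 and 14.3.1.9 use a window tied to the wrong drug for their purpose and lack the repeats given to comparable displays. What is lost is the by-term summary of prednisone-attributed events starting more than 60 days after the last IMP dose. Events, data and listings are intact.

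For a participant stopped early for treatment failure, the gap is 57-68% of the time to week 36, or 64-73% if followed to week 43 without rollover. These figures rest on the assumed last dose at weeks 3 to 7 and on the participant staying in the study, which the protocol encourages but cannot ensure. They do not describe later stoppers, such as a participant stopped for a second relapse at around week 20 (21% to week 36), or completers (none).

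The percentages, though not necessarily the participant-year rates, are understated more in an arm with more early failures. The direction and size of any between-arm distortion are unknown. Only 14.3.1.9 carries a topline consequence.

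**What to change.** Keep the TEAE versions of 14.3.1.6 and 14.3.1.9. Repeat both for post-TEAEs and for all events in the treatment and follow-up phases, as SAP 5.1.3 already does for the overview and the all-cause by-term summary. Use the post-TEAE and overall person-time denominators already defined in SAP 5.1.2. At topline, show the overall version of 14.3.1.9 beside the TEAE version. Add a footnote stating which window each version uses and that the TEAE window follows IMP, not prednisone.

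The cost is a few extra tables and the footnote. No new data, derivations or changes to conduct are needed. Replacing the TEAE versions is unnecessary and would put these two tables out of line with the other by-term tables.
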